A single-center randomized, double-blind controlled trial of  
Transcutaneous Vagus Nerve stimulation (ta-VNS) for improvement  
of upper extremity motor function in stroke patients

Title	A single-center randomized, double-blind controlled trial of Transcutaneous Vagus Nerve stimulation (taVNS) for improvement of upper extremity motor function in stroke patients
Application	Department of Rehabilitation, Zhujiang Hospital, Southern Medical University
Purpose	Primary objectives: To investigate the facilitative effect of transcutaneous auricular vagus nerve stimulation with upper limb motor rehabilitation training on the improvement of upper limb motor function in stroke. Secondary objective: To examine the necessity of pairing with motor function training for transcutaneous auricular vagus nerve stimulation to improve upper limb dysfunction in stroke.
Research hypothesis	1) The test group will show significantly greater improvement in upper limb motor function in stroke patients compared to the control group. 2) Upper limb motor rehabilitation training paired with transcutaneous auricular vagus nerve stimulation will be significantly more effective in improving upper limb motor function in stroke patients compared with the unpaired test group.
Design	Exploratory single-center, double-blind, randomized controlled trial
Sample size	Sample size was determined: $n = 2 * [(Z\alpha + Z\beta)\sigma/d]^2$ (sample size estimated using the statistical effect force analysis software G*Power3.1). The sample size for this study was estimated as 40 study patients per group based on the effect size (effect size, Cohend's $d = 0.632$ ) and $\alpha = 0.05$ , $\beta = 0.80$ from the trial by Dawson et al. (2021). The sample size was adjusted to 50 patients per group based on the clinical sample dropout rate (20%). The final study population was 150 patients with ischemic stroke. Of these, 50 received upper extremity motor rehabilitation paired with transcutaneous auricular vagal stimulation, 50 received upper extremity motor rehabilitation with unpaired transcutaneous auricular vagal stimulation, and 50 received upper extremity motor rehabilitation paired with sham-stimulation (control group).

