	
2. Secondary endpoints: ANOVA, paired samples t-test, independent samples t-test
 
(1) Paired-samples t-tests will be performed before and after the intervention for WMFT, Brunnstrom scale, Modified Barthel Index, FTHUE-HK, and EMG characteristics to compare whether there will be significant changes before and after the intervention. Since this statistical manipulation is based on multiple comparisons and there would be a bias for alpha inflation, and the statistical results will be corrected based on Bonferroni's principle.
 
(2) The WMFT, Brunnstrom scale, Modified Barthel Index, FTHUE-HK, and EMG characteristics before and after the intervention were summed and subtracted. To obtain the WMFT, Brunnstrom assessment, ADL, FTHUE-HK, and changes in EMG characteristics of the indicators before and after the intervention (i.e., secondary intervention effects), and the secondary intervention effects of the three groups were subjected to a one-way three-level (paired vs. unpaired vs. pseudo-stimulation) multiple test analysis of variance (Multivariate ANOVA) to obtain the variability of the secondary intervention effects in the three groups.
 
3) The WMFT, Brunnstrom scale, Modified Barthel Index, FTHUE-HK, and change in EMG characteristics of the paired and unpaired test groups will be tested by independent samples t-tests to obtain the difference of secondary intervention effects between paired and unpaired groups. To compensate the alpha inflation bias, the statistical results will be corrected based on Bonferroni's principle.

--	--

#Table 1 Schematic timeline of the study

TIMEPOINT	Enrollment	Allocation	Post-Allocation				Close-out
	ts	t0	t1	t2	t3	t4	t5
Enrolment	×						
Eligibility screen	×						
Informed consent	×						
Demographic information	×						
Medical history	×						
Vital signs	×		×	×	×	×	×
Randomization		×					
Allocation		×					
Interventions							
Paired ta-VNS				×			

ta-VNS	×						
Sham ta-VNS	×						

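### Secondary scales are analysed as unadjusted change scores, and sham enters their between-group comparison only through one joint MANOVA

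*Protocol*

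**What the plan says.** The Secondary endpoints part of the protocol's Statistical method has three steps.

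- Step (1) is within patients: "Paired-samples t-tests will be performed before and after the intervention for WMFT, Brunnstrom scale, Modified Barthel Index, FTHUE-HK, and EMG characteristics", with a Bonferroni correction.
- Step (2) forms change scores: "The WMFT, Brunnstrom scale, Modified Barthel Index, FTHUE-HK, and EMG characteristics before and after the intervention were summed and subtracted". I read this as post minus pre. The changes then go into a "one-way three-level (paired vs. unpaired vs. pseudo-stimulation) multiple test analysis of variance (Multivariate ANOVA").
- Step 3) takes the same changes in the two active arms, which "will be tested by independent samples t-tests to obtain the difference of secondary intervention effects between paired and unpaired groups". It adds: "To compensate the alpha inflation bias, the statistical results will be corrected based on Bonferroni's principle". The number of tests in the correction is not given.

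No step adjusts for the baseline value or uses an ordinal method. The protocol does not describe the levels of Brunnstrom or FTHUE-HK, gives no baseline distribution, and states no rule for missing components. The Design row labels the trial exploratory.

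**The concern.** The first research hypothesis is active stimulation against control. On the secondary scales, the specified tests answer that question only jointly. One MANOVA p-value does not say which scale moved, in which direction, or whether paired or unpaired stimulation differs from sham. In its standard form it also uses only patients with every component present, so an unusable EMG recording would remove that patient's clinical scales from the only between-group test containing sham.

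There is also a question of efficiency. On a scale with few levels, a patient who starts at the top can only be scored as unchanged or worse. An unadjusted change score treats that patient like one who had room to improve and did not. A model that conditions on the baseline level does not.

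**Working it through.** **1. Where sham appears**

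| Step | Test | Between-group? | Includes sham? | One result per scale? |
|---|---|---|---|---|
| (1) | paired t-test | no | not a group comparison | yes |
| (2) | MANOVA, three arms | yes | yes | no |
| 3) | independent t-test | yes | no | yes |

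No row has yes in all three columns.

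**2. The plan's own sample size.** With the Sample size row's formula, d = 0.632, two-sided alpha 0.05 and power 0.80 (sidedness assumed; the stated beta of 0.80 read as power): 2 × [(1.960 + 0.842)/0.632]² = 39.3, so 40 per arm, and 40/(1 − 0.20) = 50. This reproduces. The protocol gives no power figure for any secondary scale.

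**3. Complete cases in a five-component MANOVA.** Let q be the assumed missing share per component, independent across components. The share kept is (1 − q)^5, applied to the 40 evaluable per arm.

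| q | Kept | Of 40 |
|---|---|---|
| 3% | 0.97^5 = 0.859 | 34 |
| 5% | 0.95^5 = 0.774 | 31 |
| 10% | 0.90^5 = 0.590 | 24 |

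For scale, a univariate two-arm contrast at d = 0.632 (not tied by the protocol to any secondary scale) has 79.7% power at 40 per arm by the noncentral t, 68.7% in the 5% row and 56.6% in the 10% row. If the same patients lack everything because a visit was missed, the MANOVA loses almost no one beyond those already missing. If EMG contributes more than one feature, there are more than five components and the independent-missingness loss is larger.

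**4. Change score against baseline-adjusted models.** All inputs are assumptions: 6 ordered levels, 40 per arm, two-sided 0.05.

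- Set-up A: latent post = baseline + 0.3 + effect + N(0, 0.5); effects 0.3 and 0.4; 400 runs per cell. Top-heavy means 42% in the top level at entry.
- Set-up B: latent baseline-to-follow-up coefficient 0.8, latent SD 1, common gain 0.6, effect 0.4. The variance of latent change is (0.8 − 1)² + (1 − 0.8²) = 0.40, SD 0.632, so the standardised effect is 0.4/0.632 = 0.632, the protocol's d. A t-test on the uncut latent change had 80% to 82% power. There were 1,500 to 2,000 runs, but only 200 to 300 for proportional odds.

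| Scenario | t-test on change | Adjusted linear | Adjusted proportional odds | Gap, last minus first (points) |
|---|---|---|---|---|
| A, spread, 0.3 | 51.2% | – | 56.2% | 5.0 |
| A, spread, 0.4 | 80.0% | – | 84.2% | 4.2 |
| A, top-heavy, 0.3 | 37.2% | – | 50.2% | 13.0 |
| A, top-heavy, 0.4 | 48.2% | – | 70.0% | 21.8 |
| B, 62% at top after treatment | 32.2% | 53.7% | 56.5% | 24.3 |
| B, mid-scale (24% at top) | 60.0% | 68.9% | 72.5% | 12.5 |
| B, 22% at lowest level | 65.8% | 66.2% | 70.3% | 4.5 |
| B, 38% at lowest level | 58.3% | 57.3% | 58.0% | −0.3 |

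Simulation error is about 2.5 points (one standard error) per cell in A. For proportional odds in B the 95% margin is up to 1.96 × √(0.565 × 0.435/200) = 6.9 points.

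**5. How much is baseline adjustment alone.** In B the linear model recovers 21.5/24.3 = 88% of the gap near the top and 8.9/12.5 = 71% mid-scale. Set-up A top-heavy, repeated with separately chosen cut points and 500 runs (t-test / adjusted linear / proportional odds), gave 38/43/51 and 49/58/68, so 5/13 = 38% and 9/19 = 47%. A 200-run repeat gave 31/40/45 and 52/68/72, so 9/14 = 64% and 16/20 = 80%. A Mann-Whitney test on the change score in B was no better than the t-test in any scenario (28%, 58%, 64% and 56%, in table order).

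**6. Type I error.** The t-test on change gave 4.5% to 5.5% in A and 4.5% to 5.4% in B (6 and 7 levels). Proportional odds gave 6.2% to 6.8% in A, where the standard error is √(0.05 × 0.95/400) = 1.1 points, and 5.0% in one B check of 300 runs.

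**The case against.** The case against is substantial, and most of it narrows the point.

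- **Ordered stages.** The protocol nowhere says that Brunnstrom or FTHUE-HK are ordered stages. That stands, so the power argument is conditional on it. Brunnstrom is also absent from the secondary outcomes in the Evaluating indicator row, although Table 1 and the Statistical method include it.
- **Invalid tests.** A reader might infer that t-tests on such scales are invalid. The simulations do not support this: type I error holds, and the issue is efficiency.
- **Both ends of the scale.** A reader might infer a loss at floor and ceiling alike. Near the floor it is about nil. The large gaps need many patients near the top, and the protocol gives no baseline distribution. The eligibility criteria ask for unilateral upper limb dysfunction and state no upper limit on function, so they neither establish nor exclude such a ceiling.
- **Ordinality as the whole cause.** Comparing an unadjusted t-test with an adjusted ordinal model mixes two changes. Between roughly 40% and 90% of the gap is recovered by adjustment alone.
- **Discarding patients.** A reader might infer that the protocol orders patients without EMG to be dropped. It states no complete-case rule, the SAP is not shown, and steps (1) and 3) need no complete vector. The loss follows only from a standard MANOVA.
- **Wording of step (2).** The heading also lists ANOVA, and "multiple test analysis of variance (Multivariate ANOVA") could loosely mean several univariate tests. The complete-case issue would then disappear. A three-level omnibus test per scale would still give no active-versus-sham estimate and no baseline adjustment.

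What remains is the gap in step 3), which covers only the two active arms, and the unadjusted change score.

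**Conclusion.** The point holds in limited form. As specified, no secondary scale has its own active-versus-sham estimate; this rests on the text alone. The other two parts are conditional. Retention of 86% to 59% needs a standard MANOVA and independent missingness of 3% to 10% per component, and the extra loss is near nil if whole visits are missed. The power loss of roughly 4 to 25 points needs few ordered levels and depends on the unknown baseline distribution; near the floor it is about nil.

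Severity is minor. Only secondary outcomes of an exploratory trial are affected. A reader might carry the criticism over to the main result, but the primary FMA-UE analysis and the 40-to-50 per arm calculation do not depend on these steps.

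**What to change.** Replace the step (2) MANOVA and the step 3) t-tests with a separate three-arm model for each secondary endpoint: post-intervention value on arm and baseline value, using all patients with that endpoint. From each model report paired versus sham, unpaired versus sham and paired versus unpaired, with 95% confidence intervals and the Bonferroni correction already planned.

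Use a linear model for WMFT, Modified Barthel Index and each EMG feature. Use a proportional-odds model for Brunnstrom and FTHUE-HK, or a baseline-adjusted linear model if the proportional-odds assumption fails.

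This changes wording only and needs no new data, because baseline values are already collected. There are three costs. Two scales would be reported as odds ratios rather than mean stage differences. The proportional-odds assumption needs a check. The Bonferroni family must be counted explicitly: with EMG as one endpoint, step 3) has 5 comparisons (0.05/5 = 0.01 each), whereas three contrasts on five endpoints make 15 (0.05/15 = 0.0033 each) if all are placed in one family.

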	
2) Unpaired taVNS: -Intervention: Upper extremity motor rehabilitation training will be conducted with unpaired taVNS. The stimulator will be placed on the patient's left ear. Patients will receive 30 minutes of stimulation, with pulses of 500 ms occurring every 5-7 seconds. A total of 300 stimulations will be completed with pulses of 500 ms. After that motor training will be performed. The motor training will be identical to that of the paired group. The amplitude of the electrical stimulation will be adjusted under patients' pain threshold. The intervention will be conducted once a day, with 30 minutes of stimulation followed by 30 minutes of motor training each time for 14 days.
 
3) Sham taVNS: Upper limb motor rehabilitation training will be conducted with paired taVNS sham-stimulation. The stimulator will be placed on the patient's left ear. The amplitude of the electrical stimulation will be adjusted at 0 mA. The intervention will be conducted once a day for 40-60 minutes for 14 days.

Evaluating indicator	
Primary outcome: The score of Fugl-Meyer Assessment of Upper Extremity (FMA-UE) will be tracked before and after the intervention in the paired taVNS, unpaired taVNS, and sham taVNS groups.
 
Secondary outcome: Changes in ADL (Modified Barthel Index), the Hong Kong version of the Functional Test for the Hemiplegic Upper Extremity (FTHUE-HK), Wolf Motor Function Test (WMFT), EEG, and EMG features will be tracked after the intervention among participants.

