Statistical method	
1. Primary endpoints: ANOVA, paired-sample t-test, and independent-sample t-test will be used.
 
(1) For the main efficacy index FMA-UE scores, paired sample t-test will be performed before and after the intervention to compare whether there will be a significant change before and after the intervention. Since this statistical operation is based on multiple comparisons, there may be a bias of alpha inflation. Therefore, the statistical results will be corrected based on Bonferroni's principle.
 
(2) The FMA-UE scores before and after the intervention will be summed and subtracted to obtain the FMA-UE change scores of the indicators before and after the intervention (i.e., the main intervention effect), and a one-way three-level (paired vs. unpaired vs. pseudo-stimulated) analysis of variance (ANOVA) will be performed on the main intervention effect of the three groups to obtain the variability of the main intervention effect of the three groups.
 
(3) Independent samples t-tests will be conducted for the main intervention effects among groups. The main intervention effects of the two experimental groups will be obtained. And the main intervention effects of the paired experimental group and the unpaired experimental group will be compared by independent sample t-test.

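### On the secondary endpoints sham enters only an omnibus three-group MANOVA; the one pairwise test is paired versus unpaired, so nothing planned isolates taVNS against sham on a named outcome

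*Protocol*

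**What the plan says.** The protocol's Research hypothesis entry puts the comparison with control first: "The test group will show significantly greater improvement in upper limb motor function in stroke patients compared to the control group". Under Sample size, the control is the sham arm: "50 received upper extremity motor rehabilitation paired with sham-stimulation (control group". Paired against unpaired stimulation is the second hypothesis and the secondary objective.

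Under Statistical method, item 2 (Secondary endpoints), there are three steps for WMFT, Brunnstrom, Modified Barthel Index, FTHUE-HK and EMG characteristics:

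- Step (1): paired t-tests within arms, "to compare whether there will be significant changes before and after the intervention", with Bonferroni correction.
- Step (2): a three-level analysis of the change scores that includes sham, described as a "multiple test analysis of variance (Multivariate ANOVA) to obtain the variability of the secondary intervention effects in the three groups".
- Step 3): independent-samples t-tests, Bonferroni corrected, "to obtain the difference of secondary intervention effects between paired and unpaired groups".

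For the primary endpoint, item 1, step (3) is wider. It states "Independent samples t-tests will be conducted for the main intervention effects among groups" before it singles out paired versus unpaired.

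**The concern.** The pairwise tests written for the secondary endpoints serve only the second hypothesis. The first hypothesis is about upper limb motor function against control, and WMFT and FTHUE-HK are upper-limb function measures. Yet followed as written, the plan yields no test, estimate or confidence interval for taVNS minus sham on either of them, or on daily living or EMG.

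The other planned steps do not supply it. The within-arm tests cannot separate stimulation from recovery and training, because patients enter from two weeks after onset and every arm trains. The three-group analysis can show that the arms differ somewhere, but not which arms differ or in which direction. A real benefit of taVNS over sham on a secondary outcome could therefore pass without a planned test that shows it.

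**Working it through.** **1. Which contrasts are planned.**

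| Contrast | FMA-UE (item 1) | Secondary endpoints (item 2) |
|---|---|---|
| Three groups, omnibus | one-way ANOVA | MANOVA |
| Paired vs unpaired | t-test, named | t-test, named |
| Paired vs sham | covered by t-tests among groups | none |
| Unpaired vs sham | covered by t-tests among groups | none |

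Pairwise sham contrasts planned: 0 for each of the 5 analysed secondary measures.

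**2. The plan's own figures.** Inputs from the Sample size entry: d = 0.632, alpha 0.05, 0.80 (labelled beta, read here as power), 20% dropout. Two-sided, by the protocol's formula:

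n = 2 × [(1.960 + 0.842) / 0.632]² = 39.3, so 40 per group; 40 / (1 − 0.20) = 50; 3 × 50 = 150.

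The stated figures reproduce. A one-sided test would give 31, so two-sided is taken below. They carry no allowance for the secondary tests.

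**3. What the omnibus test can tell.** As a univariate analogue, take a one-way ANOVA with n = 40 per arm, alpha 0.05, and F on 2 and 117 degrees of freedom. The noncentrality is λ = n × Σ(mean − grand mean)², in SD units.

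- Both taVNS arms exceed sham by d: deviations d/3, d/3, −2d/3; sum of squares 2d²/3.
- Only the paired arm exceeds the other two by d: deviations 2d/3, −d/3, −d/3; sum of squares 2d²/3.
- Paired equals sham and unpaired is lower by d: deviations d/3, −2d/3, d/3; sum of squares 2d²/3.

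In all three, λ = 40 × (2/3) × 0.632² = 10.65 and power is 83.0%. The test rejects equally often whether both taVNS arms beat sham, only one does, or the paired arm does not beat sham at all.

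**4. What the one pairwise test adds.** In the first pattern the true paired-minus-unpaired difference is zero, so the test rejects only at its alpha, although both arms beat sham. In the second and third patterns the true difference is d in favour of paired, so the t-test also behaves identically in the two. Yet paired exceeds sham by d in one and by nothing in the other. The planned between-group tests together do not recover the sham comparison.

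**5. Cost of adding it.** Two-sided t-test, 40 per arm, 78 degrees of freedom, noncentrality 0.632 × √(40/2) = 2.826. Assumptions: d = 0.632 also holds for a secondary outcome (the protocol gives no secondary effect size), and EMG counts as one measure.

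| Tests in the Bonferroni family | Threshold | Power per test |
|---|---|---|
| 1 | 0.05 | 79.7% |
| 5 (5 measures × 1 contrast) | 0.010 | about 58% |
| 10 (5 × 2) | 0.005 | 47.9% |
| 15 (5 × 3) | 0.0033 | 42.6% |

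**The case against.** Four points deserve weight.

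First, a reader might infer that the trial never answers taVNS against sham. The documents do not support that. FMA-UE is the designated primary measure, and t-tests among groups are planned for it. Sham also enters the secondary MANOVA. The gap is confined to a contrast that isolates sham on a named secondary outcome. Nor does the first hypothesis promise superiority on the Modified Barthel Index or EMG.

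Second, a reader might infer that a significant MANOVA could reflect a difference between paired and unpaired alone. It cannot: if those two means differ, sham cannot equal both. What stands is that the result neither locates nor signs the difference.

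Third, the wording of step (2) is loose and could mean a separate ANOVA for each endpoint. The omnibus result would then identify the endpoint, but still not the arms, so the gap remains.

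Fourth, the trial is labelled exploratory, and follow-up contrasts, intervals and family size are often left to a statistical analysis plan, which is not shown here. Nothing in step 3) forbids further contrasts. This would be decisive if the protocol were silent on pairwise tests. It is not: it specifies them, corrects them for multiplicity and names one contrast. A later sham contrast would be an addition to a stated rule and would enlarge its Bonferroni family.

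**Conclusion.** The point holds in limited form. For WMFT, Brunnstrom, Modified Barthel Index, FTHUE-HK and EMG, sham enters only an omnibus comparison, the only pairwise between-group test written is paired versus unpaired, and no planned test or estimate isolates taVNS against sham on any one of them. The omnibus test cannot substitute: its 83.0% power is the same under patterns with opposite answers to the sham question. That figure comes from the univariate case at 40 per arm and 0.632 SD; the point that the test does not locate or sign a difference needs no such assumption.

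The primary analysis is not affected. The point is worth correcting because the fix is specific and cheap, but it concerns secondary endpoints of an exploratory trial. The power figures describe the cost of the fix, not the harm of the gap. If EMG contributes several features, the families are larger and power per test lower.

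**What to change.** In item 2, step 3), add paired versus sham for each secondary endpoint, reported as an estimate with a confidence interval, and keep paired versus unpaired. Add unpaired versus sham if a claim for that arm is intended, since two arms receive taVNS. Apply Bonferroni over all endpoints and contrasts and state the count: 10 tests with two contrasts, 15 with three, counting EMG as one measure.

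This needs no new patients or assessments. The price is a stricter threshold, which also applies to the existing paired-versus-unpaired tests: 0.005 or 0.0033 instead of 0.010. On the assumptions above, power per test falls from about 58% to 48% or 43%. The estimates and unadjusted intervals themselves do not depend on the family size.

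### Plain Bonferroni on the paired-versus-unpaired secondary tests gives up some power for no gain in error control; Holm over the same tests is a low-cost improvement

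*Protocol*

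**What the plan says.** The Protocol's Statistical method, 2. Secondary endpoints, item 3) compares the paired and unpaired groups on four clinical scales and on EMG measures: "WMFT, Brunnstrom scale, Modified Barthel Index, FTHUE-HK, and change in EMG characteristics of the paired and unpaired test groups will be tested by independent samples", meaning two-sample t-tests. It then sets the correction: "To compensate the alpha inflation bias, the statistical results will be corrected based on Bonferroni's principle". Item (1) of the same section applies Bonferroni in similar words to the before-after tests.

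The text does not state the number of tests, the divisor or the boundaries of the family. The EMG measures appear in the plural and are not listed. The Evaluating indicator row says only that "EEG, and EMG features will be tracked after the intervention among participants".

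The Sample size row gives 40 evaluable patients per group, raised to 50 for 20% dropout, using d = 0.632 and alpha = 0.05. No power is claimed for any secondary endpoint. The Design row reads "Exploratory single-center, double-blind, randomized controlled trial".

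**The concern.** The method of correction is fixed in the protocol itself, so it is not a detail waiting for an analysis plan. Among procedures that need no assumption about how the endpoints are correlated, plain Bonferroni is never better than Holm at rejecting false null hypotheses. Holm holds the same familywise error rate, uses the same p-values and needs no further data.

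The tests concerned bear on research hypothesis 2, that paired stimulation does better than unpaired. The secondary scales would support or qualify the FMA-UE result on that question. Each of them is tested at a stricter threshold than the one the trial was sized for, so power given up for nothing is worth recovering if recovery costs one sentence.

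**Working it through.** **Inputs from the Protocol (Sample size row).** d = 0.632; alpha = 0.05; power 0.80 (printed as beta = 0.80 and read as power); 40 evaluable per group; 20% dropout.

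**Inputs assumed.** Two-sided tests; d = 0.632 or d = 0.5 carried over to the secondary endpoints; k = 1, 5, 10 or 20 EMG features, since no number is given; correlation between endpoints of 0 or 0.5; one pooled family of m = 4 + k tests.

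**Step 1: the plan's own figure.** n = 2[(1.960 + 0.842)/0.632]² = 39.3, rounded up to 40 per group. Then 40/(1 − 0.20) = 50. Both stated figures reproduce with a two-sided alpha.

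**Step 2: Bonferroni at 40 per arm.** The test statistic has mean d√(n/2), which is 0.632 × √20 = 2.826. Power is close to Φ(2.826 − z), where z is the two-sided critical value at 0.05/m.

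| Tests m | Threshold 0.05/m | z | Power per endpoint, d = 0.632 |
|---|---|---|---|
| 1 (unadjusted) | 0.05 | 1.960 | 0.81 |
| 5 (k = 1) | 0.0100 | 2.576 | 0.60 |
| 9 (k = 5) | 0.0056 | 2.773 | 0.52 |
| 14 (k = 10) | 0.0036 | 2.914 | 0.47 |
| 24 (k = 20) | 0.0021 | 3.078 | 0.40 |

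The noncentral t gives slightly lower values (0.58, 0.49, 0.43 and 0.37 for the last four rows). With d = 0.5 the mean is 0.5 × √20 = 2.236, and power at m = 5 is 0.37.

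**Step 3: the Holm rule.** Order the p-values from smallest to largest and reject the i-th while p(i) ≤ 0.05/(m − i + 1), stopping at the first failure. For m = 5 the thresholds are 0.0100, 0.0125, 0.0167, 0.0250 and 0.0500. The first is Bonferroni's and the others are larger, so anything that Bonferroni rejects Holm rejects too. Control of the familywise error rate needs no assumption about dependence.

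**Step 4: the gain over the same tests, five endpoints, correlation 0.5** (simulation with normal test statistics, 40 per arm).

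| Scenario | Bonferroni | Holm |
|---|---|---|
| All five at d = 0.632, power per endpoint | 0.60 | 0.70 |
| All five at d = 0.5, power per endpoint | 0.37 | 0.44 |
| No effect anywhere, familywise error | about 0.04 | about 0.04 |

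**Step 5: the gain if only the four clinical scales respond (d = 0.632) and every EMG feature is null.** Power per clinical scale, independent endpoints:

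| EMG features k | Bonferroni | Holm | Gain, points |
|---|---|---|---|
| 1 | 0.60 | 0.67 | about 7 |
| 5 | 0.52 | 0.55 | 2 to 3 |
| 10 | 0.47 | 0.48 | about 1 |
| 20 | 0.40 | 0.41 | under 1 |

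Correlation of 0.5 changes these by less than a point. Holm helps in proportion to how many of the endpoints are really affected.

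**Step 6: what a separate EMG family would do.** With the four scales in one Holm family at 0.05 and EMG in another at 0.05, power per clinical scale is about 0.74 for every k (independent endpoints). The familywise error over all the tests is then 1 − 0.95² = 0.0975 if the families are independent and is bounded by 0.05 + 0.05 = 0.10. Simulation gives 0.094 to 0.099 at correlation 0 and 0.067 to 0.082 at 0.5. Splitting alpha as 0.025 + 0.025 brings the total back to at most 0.05, with clinical power about 0.63. That is below pooled Holm when k = 1 (0.67) and above it for larger k.

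**The case against.** The strongest reply is that nothing here is wrong. Bonferroni is valid under any dependence, is simple to explain and has simple simultaneous confidence intervals, which Holm lacks. The endpoints are secondary, no power is claimed for them, and the trial calls itself exploratory. The gains also rest on assumed effects: d = 0.632 was given for sizing the trial and not for any secondary scale, and where many EMG features are null Holm adds almost nothing. All of this stands, and it is why the point is one of efficiency and of low weight. It does not remove the fact that, for the tests themselves, Holm gives at least as many rejections at the same error rate.

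Two stronger readings are tempting, and the document supports neither.

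- A reader might infer that an open-ended set of EMG features is bound to lower the threshold for the clinical scales, as in the falling column of Step 2. That needs a single pooled family with an unfixed count. Pooling is the natural reading of item 3), but it is not stated, and the family definition and feature list may properly sit in an analysis plan that is not shown.
- A reader might infer that moving EMG to its own family is a free gain. Step 6 shows that it is not. The same error rate holds within each family only, and over all the tests it can approach 0.10. Most of the rise from 0.47 to 0.74 with ten null EMG features comes from taking EMG out of the joint control, since pooled Holm moves 0.47 only to 0.48.

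**Conclusion.** The point holds as a low-severity improvement. Over whatever set of tests item 3) is meant to cover, Holm keeps the familywise error rate at 0.05 and never rejects less than Bonferroni. The gain is about 7 to 10 points of power per endpoint if all five endpoints respond. If only the clinical scales respond, it runs from about 7 points down to under 1 as null EMG features increase from 1 to 20.

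The existence of the gain does not depend on assumptions, but its size does: 40 evaluable per arm, the effect sizes carried over, the EMG counts and the correlations of 0 to 0.5. The FMA-UE analysis is unaffected.

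**What to change.** In Statistical method, 2. Secondary endpoints, item 3), replace Bonferroni by Holm's step-down procedure over the same set of tests, and report unadjusted 95% confidence intervals beside the Holm-adjusted p-values. This costs one sentence, to be settled before unblinding. The price is that the intervals will not correspond exactly to the adjusted tests.

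Separating EMG from the clinical scales is optional and is the sponsor's decision. If it is done, the plan should either split alpha between the two families or declare EMG exploratory with no claims attached. Otherwise it should state that control is per family, with an overall error rate that can approach 0.10.
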